7.6 Data Collection for Ongoing Pregnancy Ultrasound Test

The ultrasound test to verify ongoing pregnancy is done between gestational weeks 10 and 12 for subjects who are confirmed as being pregnant at ultrasound scan during gestational weeks 6 to 8. The following information is recorded in the **LPS and**

Clinical Outcome eCRF:

• Date of the last ultrasound test for ongoing pregnancy;

Result

Number of intrauterine viable fetus;

- Spontaneous Miscarriage (miscarriage after the initial confirmation of

clinical pregnancy).

Conclusion of the clinical outcome (ongoing pregnancy or miscarriage) is recorded on the **Trial Exit eCRF** as well.

7.7 Adverse Events and Assessment of Safety

An adverse event or a serious adverse event, whether or not related to the investigational medical device, in subjects participating in the study, is not applicable. In addition, according to European Guidelines for post-marketing device studies (MEDDEV 2.12/2 rev2, dated January 2012), reporting of serious adverse events to Health Authorities is not applicable. Given the design of this study and the reporting period for safety surveillance, assessment of serious adverse device effects in offspring of subjects participating in the trial is not applicable (see Section 7.7.1

Safety of GERI+ system will be evaluated by the assessment of routine embryological data collected in the eCRF (See Section 7.7.3), and by reporting of device deficiencies (See Section 7.7.4).

7.7.1 Definitions

Definitions).

As per the European Guidelines on medical devices (MEDDEV 2.7/3 REV 3), dated May 2015:

Investigational medical device

Protocol Version: 3.0 / Jan 31, 2018 28 / 49

trial

Medical device being assessed for safety or performance in a clinical investigation NOTE: This includes medical devices already on the market that are being evaluated for new intended uses, new populations, new materials or design changes.

Adverse Event (AE)

Any untoward medical occurrence, unintended disease or injury or any untoward clinical signs (including an abnormal laboratory finding) in subjects, users or other persons whether or not related to the investigational medical device.

NOTE 1: This definition includes events related to the investigational device or the comparator.

NOTE 2: This definition includes events related to the procedures involved.

NOTE 3: For users or other persons, this definition is restricted to events related to investigational medical devices.

Serious Adverse Event (SAE)

Adverse event that:

- a) led to a death, injury or permanent impairment to a body structure or a body function.
- b) led to a serious deterioration in health of the subject, that either resulted in:
 - a life-threatening illness or injury, or
 - a permanent impairment of a body structure or a body function, or
 - in-patient hospitalization or prolongation of existing hospitalization, or
 - in medical or surgical intervention to prevent life threatening illness
- c) led to foetal distress, foetal death or a congenital abnormality or birth defect.

NOTE 1: Planned hospitalization for pre-existing condition, or a procedure required by the Clinical Investigation Plan, without a serious deterioration in health, is not considered a serious adverse event.

Device deficiency

Inadequacy of an investigational medical device related to its identity, quality, durability, reliability, safety or performance. This may include malfunctions, use error, or inadequacy in the information supplied by the manufacturer.

Adverse Device Effect (ADE)

Protocol Version: 3.0 / Jan 31, 2018 29 / 49

trial

Adverse event related to the use of an investigational medical device.

NOTE 1- This includes any adverse event resulting from insufficiencies or inadequacies in the instructions for use, the deployment, the implantation, the installation, the operation, or any malfunction of the investigational medical device.

NOTE 2- This includes any event that is a result of a use error or intentional abnormal use of the investigational medical device.

Serious Adverse Device Effect (SADE)

Adverse device effect that has resulted in any of the consequences characteristic of a serious adverse event.

Unanticipated Serious Adverse Device Effect (USADE)

Serious adverse device effect which by its nature, incidence, severity or outcome has not been identified in the current version of the risk analysis report.

NOTE: Anticipated SADE (ASADE): an effect which by its nature, incidence, severity or outcome has been previously identified in the risk analysis report.

7.7.2 Reporting period for safety surveillance

The reporting period for safety surveillance begins when the subject is included into the trial (date of randomization) and continues after embryo transfer until achievement of ongoing pregnancy. There is no live birth follow-up planned in the frame of this study.

7.7.3 Safety assessment of embryological data

To comprehensively evaluate the safety of GERI+ embryo culture system, as provided by the GERI+ incubator, we will monitor the following secondary endpoints/parameters which are closely related to the quality and viability of embryos and report to Merck Global Drug Safety after the completion of this trial:

- The number and percentage of Good Quality Embryos per subject, in both arms of study: Good Quality Embryos are embryos with 7 or more blastomeres, <25% fragmentation, size and symmetry of blastomeres appropriate to the cell number, and no evidence of multinucleation, based on the Day 3 morphology (modified from Alpha Scientists in Reproductive Medicine and ESHRE Special Interest Group Embryology, 2011)
- The number and percentage of Non-viable Embryos per subject, in both arms of

study: Non-viable Embryos are embryos in which development has been arrested for at least 24 h or in which all the cells have degenerated or lysed (Alpha Scientists in Reproductive Medicine and ESHRE Special Interest Group Embryology, 2011).

7.7.4 Device Deficiency

Methods of recording Device Deficiencies

Investigators must inform, via the established customer complaint process, their local Merck KGaA contact, usually the Clinical Applications Engineer (CAE) in case of any device related complaint and/or deficiency. Feedback may consist of any alleged deficiency related to the physical characteristics, identity, quality, durability, reliability, effectiveness or performance of GERI+ system.

Genea Biomedx, the legal manufacturer of GERI+ system, will investigate device malfunctions/deficiencies and perform an evaluation to determine and document the root cause of any device deficiency. A final list of all device deficiencies occurring at the study sites during the course of the study will be attached to the clinical study report.

Reporting of Device Deficiencies

Investigators are responsible for reporting to Merck KGaA device deficiencies that may affect the culture and assessment process of the embryos during the course of embryo culture through trial completion. An assessment of the device deficiency by the investigator is not mandatory.

Genea Biomedx is responsible for reporting of device deficiencies to NCA (National Competent Authorities) according to applicable legal post-marketing reporting obligations for medical devices (e.g. Directive 93/42/EEC).

7.7.5 Reporting after defined reporting period for safety surveillance

Beyond the defined reporting period of this study, it is the responsibility of the investigators to inform any serious abnormal pregnancy outcome in subjects who participated in this study, including of any congenital anomalies in the offspring of these subjects, to spontaneously report the serious adverse events either directly to the

Protocol Version: 3.0 / Jan 31, 2018 31 / 49

marketing authorization holder Genea Biomedx or to their local regulatory health authorities, if necessary, as required by the local reporting guidelines.

8. STATISTICS

8.1 Sample Size

Based on an expected clinical pregnancy rate of 30% (Adamson et al., 2016) in the control group and a 25% relative increase of clinical pregnancy rate in the experimental group, a two-sided test with an alpha level of 0.05 needs 623 subjects per group to reach a power of 80%. With a drop-out rate of 10%, 1,386 subjects (693 per group) need to be randomized. A subject can be considered as a drop-out during the study if she is randomized but primary endpoint data is not available for this subject, for whatever reason.

The calculation of sample sizes was performed using nQuery Advisor® version 7.0.

8.2 Randomization

A stratified permutated block randomization with fixed block size and allocation ratio 1:1 will be used. Randomization will be accomplished using Interactive Web Response Services (IWRS) system. The stratification will be based on site and age of the subject (18-35 versus 36-40). This guarantees, at any time, a similar number of subjects between experimental and control groups at each site.

8.3 Analysis Sets

Three analysis sets will be used: the Full Analysis dataset, the Per Protocol dataset and the Subgroup Analysis dataset.

- Full Analysis (FA-) dataset includes all randomized subjects. Subjects will be presented as randomized.
- Per Protocol (PP) dataset includes all subjects who have been treated according to the Clinical Trial Protocol and have received Day 3 fresh embryo transfer, with no major Clinical Trial Protocol violation in respect of factors likely to affect the efficacy of treatment.
- · Subgroup Analysis dataset (SA):Subjects who had embryos transferred which were either good or fair (i.e. not poor quality)

32 / 49

trial

• .

The FA population is the primary analysis population. PP population is used for sensitivity analysis. SA population is used for supportive analysis.

8.4 Description of Statistical Analyses

8.4.1 General Consideration

Descriptive Statistics

For continuous variables, the following parameters will be presented: Number (N) of subjects, mean, standard deviation (SD), median, first quartile (q1), third quartile (q3), minimum, and maximum. For categorical variables, the total number ('N') of subjects and proportions will be presented. Graphical methods will be used as appropriate. Number of subjects with missing values ('Missing') will be listed for the analyses based on observed case data.

Method of handling missing data

Missing data will not be imputed.

8.4.2 Analysis of Primary Endpoint

The FHB positive clinical pregnancy rate (the number of subjects with FHB positive clinical pregnancy divided by the number of subjects with embryo transfer) for either of the two treatment groups will be computed.

Primary hypothesis will be tested between the treatment groups based on a Cochrane-Mantel-Haenzel CMH test adjusting for stratification factors providing the derived Odds Ratio and its 95% confidence interval. As sensitivity analysis, a logistic regression model with confounding factors and stratification factors as covariates will be performed. Details regarding the model and analysis will be specified in the SAP.

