6.6 Method of Blinding

- Blinding: The trial is blinded to the subjects. The trial is not blinded to the embryologists handling the embryos or the clinicians/nurses conducting embryo transfer and pregnancy tests/scans.
- Emergency Un-blinding: in case of a medical emergency, the subject will be informed by her trial doctor or embryologist which incubator and embryo grading method are used for her embryos.

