6.7 Randomization and Allocation of Subjects

After signing the informed consent form, all eligible subjects will be randomized and allocated to either of the two treatment groups immediately after fertilization check on Day 1 of embryo culture.

A stratified block randomization with fixed block length and allocation ratio 1:1 will be used. The stratification will be based on site and the age of subject (age group 18-35 vs. 36-40). Randomization will be accomplished using the Interactive Web Response Services (IWRS) system. An independent statistician will generate the

Protocol Version: 3.0 / Jan 31, 2018 21 / 49

Study Number: MS200497_0006

randomization schedule and upload to the IWRS system. All randomization codes will not be reused and subjects who discontinue the study early will not be replaced.

A subject can be considered as a drop-out during the study if she is randomized but primary endpoint data is not available for this subject, for whatever reason. Reasons for study discontinuation will be recorded in the Trial Exit eCRF.

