#### 8.2 Definition of Analysis Sets and Subgroups

#### **Full Analysis (FA) dataset:**

(FA) dataset includes all randomized subjects. Subjects will be presented as randomized.

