#### 14 Efficacy Analyses

# 14.1 Clinical Pregnancy with positive fetal heartbeat (Primary Endpoint)

The primary end point is clinical pregnancy with positive fetal heartbeat. It is defined as the pregnancy diagnosed by ultrasonographic or clinical documentation of at least one fetus with heart beat in gestational week 6 to 8. It includes ectopic pregnancy.

The qualitative variables

- Ultrasound performed (Yes/No)
- Result of ultrasound (Biochemical pregnancy/ Ectopic pregnancy/ Intrauterine clinical pregnancy (with and without positive FHB)/ Clinical pregnancy (FHB positive or negative intrauterine pregnancy + ectopic pregnancy)/ Other)
- Number of subjects with Embryo transfer attempted (Yes/No)
- Subjects with FHB positive clinical pregnancy

will be summarized by using number and percentage for both treatment groups and overall from (FA) dataset and (PP) dataset.

The quantitative variables

- Number of intrauterine gestational sacs
- Number of sacs with fetal heartbeats

will be summarized by using descriptive statistics for both treatment groups and overall from (FA) dataset and (PP) dataset.

The quantitative variable

• FHB positive Clinical pregnancy rate (%)

will be summarized by percentage for both treatment groups and overall from (FA) dataset and (PP) dataset.

No. of subjects with clinical pregnancy = Intrauterine clinical pregnancy subjects (with and without positive FHB) + Ectopic pregnancy subjects.

**Subject with FHB positive clinical pregnancy** = Intrauterine Clinical Pregnancy subject with at least one or more sacs with fetal heartbeats

FHB positive clinical pregnancy rate (%) = No. of subjects with FHB positive clinical pregnancy)/ No. of subjects with embryo transfer)\* 100.

No. of subjects with embryo transfer = Subjects with embryo transfer attempted.

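### The labelled primary pregnancy rate is per woman with embryo transfer, although all randomised women are the primary population; the SAP also lists an FA percentage, but neither figure is named as the primary result

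*Protocol*

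**What the plan says.** **The rate.** Protocol 8.4.2 computes, for each arm, "the number of subjects with FHB positive clinical pregnancy divided by the number of subjects with embryo transfer". SAP 14.1 gives the same formula and adds "No. of subjects with embryo transfer = Subjects with embryo transfer attempted".

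**The population.** Protocol 8.3 states "The FA population is the primary analysis population", and SAP 8.2 agrees. The SAP's definition is that the FA "dataset includes all randomized subjects. Subjects will be presented as randomized". By contrast, Protocol 8.3 admits to the Per Protocol set, used for sensitivity analysis, only women who "have received Day 3 fresh embryo transfer".

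**The timing.** Protocol 6.7 allocates women "immediately after fertilization check on Day 1 of embryo culture". Transfer follows on Day 3. SAP 10.1 tabulates cancelled fresh transfers by reason, including failure to cleave, no viable embryo, and freezing all embryos because of OHSS risk. Protocol 6.6 says "The trial is not blinded to the embryologists handling the embryos", and the same holds for the clinicians who perform the transfer.

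**A second percentage.** SAP 14.1 also lists "Subjects with FHB positive clinical pregnancy" among variables to be shown by number and percentage from the FA and PP sets, without writing out a denominator. The default in SAP 9 is the whole analysis set with missing values included. SAP 9 also has a rule for visit-specific analyses, based on women still in the trial at that visit.

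**Inference.** Protocol 8.4.2 plans a CMH test but does not say which women enter it. SAP 7 drops all group comparisons and confidence intervals.

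**The concern.** The only formula labelled as the primary rate leaves out randomised women who do not reach transfer. Whether a woman reaches transfer is settled after randomisation, by staff who know her arm, and partly by how her embryos develop under the culture being compared. If one arm has more cancellations, those women leave its denominator and its rate rises relative to the other arm. This restriction resembles the one that Protocol 8.3 reserves for the Per Protocol set.

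Protocol 5.1 sets out to judge the clinical value of an integrated culture and assessment system, and reaching transfer is part of that value. With two percentages under one primary-endpoint heading and neither ranked, the choice between them could also be made after the results are known.

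**Working it through.** **1. The plan's own sample size.** Inputs from Protocol 8.1: 30% control; 25% relative increase, so 37.5%; two-sided alpha 0.05; 80% power; 10% drop-out. With pooled variance under the null, no continuity correction and a mean rate of 0.3375:

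n = [1.960 × √(2 × 0.3375 × 0.6625) + 0.842 × √(0.30 × 0.70 + 0.375 × 0.625)]² / 0.075² = 623 per group.

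623 / 0.9 = 692.2, rounded up to 693 per group, or 1,386 in total. The stated figures reproduce, so the sample size contains no arithmetic error. Protocol 8.1 does not say whether 30% and 37.5% are per transfer or per randomised woman, or whether a woman without transfer is a drop-out.

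**2. What each denominator contains.**

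| Figure | Denominator | Written or inferred |
|---|---|---|
| Labelled rate (Protocol 8.4.2, SAP 14.1) | Women with transfer (attempted) | Written |
| FA percentage in SAP 14.1, SAP 9 default | All randomised women | Inferred |
| FA percentage in SAP 14.1, SAP 9 visit rule | Women still in the trial at the scan | Inferred |

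The third reading matters because Protocol 6.10 has hCG-negative women exit before the scan. The second is more likely, but SAP 14.1 does not settle it.

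**3. How far the denominator can move the displayed rates.** Let c be the share of an arm without transfer. Then per-transfer rate = per-randomised rate / (1 − c). The documents give no value of c, so the following are assumptions: 28% per randomised woman in both arms (no true difference) and 693 per arm.

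| Without transfer, arm A vs B | Women without transfer (about) | Per-transfer rate, A vs B | Displayed difference |
|---|---|---|---|
| Equal | equal | equal | 0 |
| 5% vs 3% | 35 vs 21 | 29.5% vs 28.9% | 0.6 points |
| 10% vs 8% | 69 vs 55 | 31.1% vs 30.4% | 0.7 points |
| 10% vs 5% | 69 vs 35 | 31.1% vs 29.5% | 1.6 points |

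Either trial arm could be A. With equal shares the ratio is the same on both denominators: at 10%, 33.75 / 27.0 = 37.5 / 30 = 1.25.

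**4. Power if the per-randomised rate is primary.** With 693 per arm, all outcomes known, and p1 = 0.30(1 − c), p2 = 0.375(1 − c), d = p2 − p1, p̄ their mean:

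power = Φ{[d√693 − 1.960√(2p̄(1 − p̄))] / √[p1(1 − p1) + p2(1 − p2)]}.

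| Common share without transfer (assumed) | Rates per randomised woman | Power |
|---|---|---|
| 0% (planning rates already per randomised woman) | 30.0% vs 37.5% | 84.0% |
| 5% | 28.5% vs 35.6% | 81.2% |
| 10% | 27.0% vs 33.75% | 78.1% |
| 15% | 25.5% vs 31.9% | 74.7% |

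The last three rows take 30% and 37.5% as per-transfer rates.

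**The case against.** The per-transfer denominator is prespecified and internally consistent. The synopsis and SAP 5 word the endpoint as a pregnancy following a fresh Day 3 transfer. The biochemical, ongoing and ectopic pregnancy rates use the same denominator. The 10% inflation fits if cancelled transfers are drop-outs, since 693 × 0.9 = 623.7. This explains the choice, but it does not reconcile the rate with an FA primary population, because a woman without transfer can be counted as having had no such pregnancy.

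Much of the information is planned output anyway. Cancellations and reasons appear by arm (SAP 10.1), the FA percentage is probably per randomised woman, and embryo outcomes per 2PN zygote are summarised from the FA (SAP 14.2.1 to 14.2.3). A reader could therefore see an imbalance and recompute the rate. This lowers the practical weight, but the labelled rate would still not reflect the imbalance.

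An imbalance may also be small. Entry requires at least four 2PN zygotes, planned freeze-all cycles are excluded, and the GERI+ arm falls back on the control decision grid when EEVA gives no result or all embryos are poor. The shifts in step 3 compare with a standard error of about 2.6 points for the difference (√(2 × 0.30 × 0.70 / 624)).

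Three stronger readings are tempting but unsupported:
- That the plan favours GERI+. The documents give no cancellation rates, so the direction is unknown.
- That the type I error is inflated. SAP 7 removes the test, and Protocol 8.4.2 names no denominator for it.
- That the SAP has no per-randomised figure. It probably has one, unlabelled.

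**Conclusion.** The point holds as a mismatch between the labelled primary rate and the declared primary population. That rate is conditional on an event after randomisation which the intervention may influence, so it is not a comparison of the groups as randomised. The mismatch itself is plain from the text.

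Its practical size is not known. Under the assumed imbalances of 2 to 5 percentage points, the displayed difference moves by about 0.6 to 1.6 points against a planned 7.5; with equal cancellation the ratio is unbiased. While SAP 7 stands, the consequence is a shift in displayed percentages and an open choice between two figures, not a wrong test result. It should be fixed because the correction is specific and cheap, and because without tests the percentages carry the conclusion.

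**What to change.** - **Primary rate.** In Protocol 8.4.2 and SAP 14.1, name the FA percentage per randomised woman as primary. State that its denominator is all randomised women and that the visit rule in SAP 9 does not apply.
- **No transfer.** Count women with no embryo transfer as known non-events, not as drop-outs under Protocol 8.1.
- **Transfer on another day.** The endpoint wording refers to Day 3, while the SAP 14.1 denominator is any transfer attempted. Reconcile them, so that the handling of a pregnancy after a fresh transfer on another day is stated and is the same in both arms.
- **Lost after transfer.** Keep these women in the denominator and show them by arm as a separate missing category, as SAP 9 already provides. Explain how this fits the no-imputation statements in Protocol 8.4.1 and SAP 9, since they then add nothing to the numerator. Exclude them in a sensitivity analysis.
- **Supportive rate.** Keep the per-transfer rate, labelled as such.
- **Test.** If the protocol's CMH test is run, use the primary denominator.
- **Sample size.** State in Protocol 8.1 which denominator 30% and 37.5% refer to, and restate power at 693 per arm using step 4.

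Cost: a SAP revision and a protocol amendment under Protocol 10.6, with no new data. Stated power may fall below 80%: it is 78.1% if the rates are per transfer and 10% have no transfer. The current SAP is dated 14 January 2020, after the planned last patient in (December 2019). The change must therefore be documented as made before database lock and without sight of results by arm. That record should address the unblinded site staff and the test-group implantation data that the sponsor collects during the study (Protocol 10.1).

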# 7 Changes to the Planned Analyses in the Clinical Trial Protocol

The statistical methods as described in the protocol were adopted and no changes to the planned analyses. However Statistical comparison between groups and confidence intervals will not be performed. No regression models will be constructed in this study.

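### The trial is sized on a 25% relative increase in the pregnancy rate, but the only between-group estimate planned with an interval is an odds ratio, which is 1.40 for that same effect

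*Protocol*

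**What the plan says.** **Planning scale.** Protocol 8.1 starts "Based on an expected clinical pregnancy rate of 30" per cent in the control group and assumes "a 25% relative increase of clinical pregnancy rate in the experimental group". It concludes that "a two-sided test with an alpha level of 0.05 needs 623 subjects per group to reach a power of 80" per cent, and then: "With a drop-out rate of 10%, 1,386 subjects (693 per group) need to be randomized".

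**Estimation scale.** Protocol 8.4.2 first computes the pregnancy rate in each group, among subjects with embryo transfer. It then compares the groups by a "Cochrane-Mantel-Haenzel CMH test adjusting for stratification factors providing the derived Odds Ratio and its 95% confidence interval". The sensitivity analysis is also on the odds scale: "a logistic regression model with confounding factors and stratification factors as covariates will be performed". Further detail is left to the SAP.

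**SAP.** Section 7 says that the protocol's methods are adopted without change, and then continues: "However Statistical comparison between groups and confidence intervals will not be performed". It also rules out regression models. Section 14.1 gives the rate in each treatment group and overall, and no between-group measure. Neither document names a risk ratio or a risk difference.

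**The concern.** The planning hypothesis is a ratio of two rates, and the planned estimate is a ratio of two odds. When about a third of women have the event, the two measures differ noticeably and the odds ratio lies further from 1. The odds ratio and its interval therefore cannot be set directly against the 25% on which the trial was sized.

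What is at stake is the reading of the primary result. The natural questions are whether the data are compatible with a 25% relative increase, and how many percentage points the increase amounts to. Protocol 8.4.2 plans no interval that answers either directly. Under SAP section 7 as it stands there would be no interval on any scale.

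**Working it through.** **Inputs.** Control rate p1 = 0.30, relative increase 25%, two-sided alpha 0.05, power 80% and drop-out 10% (Protocol 8.1); 1:1 allocation (Protocol 8.2).

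**1. Reproduce the plan's figure.** The experimental rate is p2 = 0.30 × 1.25 = 0.375 and the mean rate is 0.3375. With pooled variance under the null and no continuity correction:

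n = [1.960 × √(2 × 0.3375 × 0.6625) + 0.842 × √(0.30 × 0.70 + 0.375 × 0.625)]² / 0.075² = [1.3107 + 0.5610]² / 0.005625 = 622.8, so 623 per group.

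After drop-out, 623 / 0.90 = 692.2, so 693 per group and 1,386 in total. Both figures match the protocol, which confirms that the planning pair is 30% and 37.5%. A Wald calculation on the log-odds scale gives 626 per group, so the choice of scale hardly affects the sample size.

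**2. The planned effect on each scale.**
- Risk ratio: 0.375 / 0.30 = 1.25.
- Risk difference: 0.375 − 0.30 = 7.5 points.
- Odds ratio: (0.375 / 0.625) / (0.30 / 0.70) = 0.6000 / 0.4286 = 1.40.

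**3. What an odds ratio of 1.25 would mean.** From a 30% control rate the experimental odds are 0.4286 × 1.25 = 0.5357. The rate is 0.5357 / 1.5357 = 34.9%. That is a risk ratio of 1.16 and a difference of 4.9 points, about two-thirds of the planned difference (4.9 / 7.5 = 0.65).

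**4. Dependence on the assumed 30%.** With the risk ratio held at 1.25:

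| Control rate | Odds ratio |
|---|---|
| 20% | 1.33 |
| 25% | 1.36 |
| 30% | 1.40 |
| 35% | 1.44 |
| 40% | 1.50 |

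The clinical pregnancy rates that Protocol 4.2 quotes from a controlled study (46.0% and 32.1%) give a risk ratio of 1.43 and an odds ratio of (0.460 / 0.540) / (0.321 / 0.679) = 1.80.

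**5. Intervals if the plan is met exactly.** These are approximate, unstratified and at 623 per group, because the documents give no stratum rates.
- Risk difference: standard error √(0.444375 / 623) = 0.0267; 95% CI 2.3 to 12.7 points.
- Risk ratio: standard error of the log √[(0.70/0.30 + 0.625/0.375) / 623] = 0.0801; 95% CI 1.07 to 1.46.
- Odds ratio: standard error of the log √[(1/0.21 + 1/0.234375) / 623] = 0.1204; 95% CI 1.11 to 1.77.

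All three exclude no effect. They describe the same data in quite different sizes.

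**6. Stratified against crude odds ratio.** An odds ratio common to all strata need not equal the crude one. Assume two equal strata with control rates of 20% and 40% and an odds ratio of 1.40 in each. The experimental rates are then 25.9% and 48.3%, mean 37.1%, and the crude odds ratio is (0.371 / 0.629) / 0.4286 = 1.38. With control rates of 25% and 35% it is 1.39. With five equal strata from 10% to 50% it is 1.35. This effect is modest beside the step from 1.25 to 1.40.

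**The case against.** The case against giving this much weight is a good one.

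- **A pair of proportions fixes all three measures, and the null is the same on each.** This stands. The CMH test is valid and the sample size holds, so a reader who inferred that either is compromised would be wrong.
- **The group rates are reported.** This stands in part. Protocol 8.4.2 and SAP 14.1 both give the rate per group, so a crude ratio or difference can be read off. What is missing is a planned, stratum-adjusted estimate with an interval.
- **The harm is hypothetical.** A reader might infer that the benefit will be overstated. The documents do not support that: the measure is correctly named as an odds ratio, and nothing says it will be judged against the 25%.
- **The odds ratio is the usual companion of a CMH test and matches the planned logistic model.** This stands. Making it secondary would be a preference, and the documents give no ground for calling it wrong. A common risk ratio or risk difference across site-by-age strata is an assumption too.
- **The stratified odds ratio might be thought to clash with the printed rates.** The documents give no stratum rates, and under the spreads tried above the discrepancy is small.
- **Under the SAP no odds ratio will be produced at all.** This is true of the text, and it is the larger problem. It does not dispose of the point: if the comparison is restored as Protocol 8.4.2 words it, only the odds ratio returns.

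**Conclusion.** The point holds as a weakness in estimation and interpretation. The trial is planned on a risk ratio of 1.25 (7.5 points), while the only between-group estimate planned with an interval is an odds ratio, equal to 1.40 at the planned effect. An odds ratio of 1.25 would correspond to a risk ratio of only 1.16, or 4.9 points. These conversions rest on the protocol's 30% control rate; for control rates of 20% to 40% the planned risk ratio corresponds to an odds ratio of 1.33 to 1.50.

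Neither document provides an interval on the planning scale, and SAP section 7 withdraws even the one that Protocol 8.4.2 promises. The case for acting is that the remedy costs almost nothing beyond a reconciliation that is needed in any event.

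**What to change.** Deal with this when SAP section 7 is reconciled with Protocol 8.4.2:

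1. Amend SAP section 7 so that the stratified between-group comparison and its confidence interval are restored. An addition to SAP 14.1 alone would contradict section 7.
2. In Protocol 8.4.2 and SAP 14.1, add the Mantel-Haenszel risk difference and risk ratio, stratified by site and age group, each with a 95% CI, beside the odds ratio.
3. State that the result will be interpreted against the planned 25% on the risk-ratio scale.

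The data and strata are those already planned, and the sample size stays at 623 per group (1,386 in total). The cost is slightly more output and the amendment of SAP section 7.
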